#### **Hematology:**

Complete blood count  
Hemoglobin  
Hematocrit  
Red blood cell count  
Mean corpuscular volume  
Mean cell hemoglobin  
Mean cell hemoglobin concentration  
Red cell distribution width  
White blood count with differential:  
- Neutrophils  
- immature granulocytes  
- lymphocytes  
- monocytes  
- eosinophils  
- basophils  
Platelets  
Hemoglobin A1c

#### **Chemistry:**

Sodium  
Potassium  
Bicarbonate  
Calcium  
Chloride  
Glucose  
Phosphate  
Creatinine  
Blood urea nitrogen  
Creatine phosphokinase  
Uric acid  
Albumin  
Alkaline phosphatase (ALP)  
Alanine amino transferase (ALT)  
Aspartate amino transferase (AST)  
Gamma glutamyl transferase (GammaGT)  
Lactate dehydrogenase (LDH)  
Total protein  
Total bilirubin

Total cholesterol  
Triglycerides

## 7 STUDY MATERIALS

### 7.1 Study Treatment(s)

#### 7.1.1 Study Treatment(s)/ Formulation(s)/ Medical Device Composition or Design

The eye drop suspensions, DexNP 1.5% w/v, consist of the following ingredients:

Dexamethasone,  $\gamma$ -cyclodextrin, disodium edetate, poloxamer, sodium chloride and purified water. All ingredients comply with their Ph. Eur. or USP monographs or both. The formula is patent protected.

The eye drop suspensions, DexNP 15 mg/ml, consist of the following ingredients:

$\gamma$ -cyclodextrin, disodium edetate, poloxamer, sodium chloride and purified water. All ingredients comply with their Ph. Eur. or USP monographs or both.

The dexamethasone cyclodextrin NP suspension eye drops and the Vehicle eye drops will be dispensed in single dose containers. An appropriate number of unit dose containers are dispensed for each patient in order to have enough medication until the next visit.

Vehicle eye drops will be prepared in identical packaging. The DexNP eye drops and vehicle will be packaged in a primary one dose vial. Secondary package will be in the foil envelopes and foil envelopes will be packaged in a box.

The dexamethasone cyclodextrin suspension eye drops and the comparator drug will be kept under controlled conditions at study sites or affiliated pharmacies where dispensing records will be kept.

#### 7.1.2 Instructions for Use and Administration

- The eye drops are milky white and in single dose units.

**Study group.**

The study eye will receive 1 DexNP eye drop 3 times a day (every 8 hrs) for 12 weeks.

**Control group.**

The study eye will receive 1 vehicle eye drop 3 times a day (every 8 hrs) for 12 weeks.

- The eye drops should be stored in their container at room temperature protected from direct sunlight.
- Directions for the use of DexNP 15mg/mL eye drops and DexNP Vehicle.
  1. Wash your hands thoroughly with soap and water.
  2. Twist off the top of the container. Check the container tip to make sure that it is not chipped or cracked.
  3. Avoid touching the container tip against your eye or anything else – eye drops and containers must be kept clean.
  4. While tilting your head back, pull down the lower lid of your eye with your index finger to form a pocket.
  5. Hold the container (tip down) with the other hand, as close to the eye as possible without touching it.
  6. Brace the remaining fingers of that hand against your face.
  7. While looking up, gently squeeze the dropper so that a single drop falls into the pocket made by the lower eyelid. Slowly remove your index finger from the lower eyelid.
  8. Close your eye for 2 to 3 minutes and tip your head down as though looking at the floor. Try not to blink or squeeze your eyelids.
  9. Place a finger on the tear duct and apply gentle pressure.
  10. Wipe any excess liquid from your face with a tissue.
  11. Keep the used container after use and return to your study site at next scheduled visit.
  12. Wash your hands to remove any medication.

## 8 STUDY METHODS AND PROCEDURES

### 8.1 Subject Entry Procedures

#### 8.1.1 Overview

Subjects as defined by the criteria in section 5.2, 5.3, and 5.4 will be included in this study.

#### 8.1.2 Informed Consent

Prior to a subject's participation in the trial (i.e., changes in a subject's medical treatment and/or study related procedures), the study will be discussed with each subject, and subjects wishing to participate must give written informed consent using an informed consent form. The informed consent form must be the most recent version that has received approval/favorable review by a properly constituted Ethics Committee.

#### 8.1.3 Washout Intervals

As per exclusion criteria, section 5.4.

IVT, subtenon, or periocular, non-sustained release, steroid therapy: 3 months prior to Visit 1 (e.g., triamcinolone)

IVT sustained release dexamethasone therapy: 6 months prior to Visit 1.

IVT sustained release fluocinolone: 3 years prior to Visit 1.

IVT afibercept: within 8 weeks and ranibizumab/bevacizumab: 6 weeks of Visit 1.

History of prior treatment for DME with any other (than previously listed) approved treatment which is not labeled for DME: 1 year prior to Visit 1.

#### 8.1.4 Procedures for Final Study Entry

Patients who have current DME and overall DME of less than 3 years duration since diagnosis will be approached by the personnel (including but not limited to nurses, optometrists, ophthalmologists) in their clinics. They will be informed about the study by qualified and trained personnel and if willing to participate, they will be asked to read and sign an informed consent form.

Participants will undergo a complete eye examination and fill out a questionnaire on medical and eye health, drug use and allergies.

Patients need to fulfill all inclusion criteria including vision as assessed by ETDRS charts and retinal thickness as assessed by SD-OCT. They must not meet any of the exclusion criteria.

#### 8.1.5 Methods for Assignment to Treatment Groups:

At visit 2, the subject will be randomized in a 2:1 ratio to active drug or the vehicle group.

### 8.2 Concurrent Therapies

The use of any concurrent medication, prescription or over-the-counter, is to be recorded on the subject's source document and corresponding case report form (CRF) along with the reason the medication was taken.

Concurrent use of other eye drops is not allowed. Should concurrent treatment with IOP lowering eye drops (prefer prostaglandin) become necessary due to increased IOP, those eye drops should be administered in the evening 15 minutes before DexNP/Vehicle eye drops.

Other treatments for DME are not allowed in the study eye while the patients are included in the study except if they meet the rescue criteria as described in 8.2.2 below.

If the fellow eye needs any treatment for DME or any other conditions, standard of care (i.e. anti-VEGF for DME) can be applied except steroids. So i.e. Ozurdex or topical dexamethasone will not be allowed for the treatment of the fellow eye during the course of the study.

The use of contact lenses is NOT allowed during the active study treatment phase of 12 weeks.

Concurrent enrollment in another investigational drug or medical device study is not permitted.

#### 8.2.1 Prohibited Medications/Treatments

Other ophthalmic formulations e.g. eye ointment, eye drops.

Other DME treatment (incl. triamcinolone, dexamethasone, fluocinolone, aflibercept, ranibizumab and bevacizumab) in the study eye

See exclusion criteria.

#### 8.2.2 Escape Medications

If IOP rises above 25 mmHg a topical prostaglandin analog will be considered. If IOP rises above 32 mmHg, the study drug will be discontinued, (DexNP or vehicle eye drops) and the IOP treated with glaucoma drugs or other treatment at the discretion of the study ophthalmologists.

If BCVA drops by 10 letters or more or CMT increases by 20% or more at 2 consequent visits and the changes are judged by the treating physician to be due to DME the patient should be stopped to receive the DexNP or vehicle experimental eye drops and may be treated at the discretion of the investigator with standard of care, i.e. anti VEGF injections or steroid implant. The patient should be asked to return for all scheduled control visits, even if the study drug has been discontinued

If BCVA drops by 10 letters at 2 consequent visits and the decrease in vision is felt by the treating physician to be due to cataract formation the patient shall be offered cataract surgery and IOL implantation. The patient stays in the study and continues with eye drops as indicated by the protocol.

### 8.3 **Examination Procedures**

#### 8.3.1 Procedures to be performed at Each Study Visit with Regard to Study Objective(s)

A complete eye examination will be performed. (Detailed descriptions may be found in an optional study manual if deemed necessary by the sponsor)

- Visual acuity will be measured at every visit using ETDRS chart at 4m with best corrective lenses.
- Intraocular pressure (IOP) will be measured at every visit with Goldmann tonometry or I-CARE tonometry (standardized in each center and the same device to be used for a given patient throughout the study)
- Eye examined at every visit by slitlamp.
- Fundus is examined at every visit through dilated pupils (i.e. using Tropicamide hydrochloride 1% and phenylephrine 2.5%),
- Fundus photographs obtained (optional)
- Optical coherence tomography (SD OCT preferably using Heidelberg Spectralis) performed at each visit to measure central macular thickness (CMT).
- In phakic eyes cataract formation will be graded using the LOCS III system.
- Irritation will be evaluated at every visit by slit lamp biomicroscopy, fluorescein staining when deemed necessary

- Blood pressure should be measured on the patient sitting for at least 2 minutes, on the right arm.
- Quality of life as assessed by NEI VFQ-25 at baseline and 12 weeks.

The full eye examination will be performed before start of the study at screening and then at each visit (Day 1, weeks 2, 4, 8, 12 and 16) until end of the study period.

#### Optional imaging

At the discretion of the investigator, additional imaging of the eye / macula can be performed for diagnostic purposes to evaluate the safety and efficacy of the experimental DexNP eye drops or vehicle while the study is ongoing, including fundus photographs, fluorescein angiography (FA) additional OCT's or angio-OCTs. All those diagnostic procedures are standard of care and used for the standard daily clinical routine diagnostic.

Adverse events will be monitored throughout the study. All adverse events will be promptly reviewed by the investigator for accuracy and completeness. All adverse events will be documented on the appropriate case report form.

If a female has a positive pregnancy test during the study, then the investigator will notify IRW Consulting immediately. The investigator shall request from the subject and/or the subject's physician copies of all related medical reports during the pregnancy and shall document the outcome of the pregnancy. The investigator will retain these reports together with the subject's source documents and will provide a copy of all documentation to IRW Consulting.

Investigating physicians will fill out a CRF where all measurements are recorded. The ophthalmologist performing the complete eye examination will be masked to which drug the patients are receiving. The patients will receive either DexNP eye drops or vehicle at the same frequency (double blind).

Participants will be asked to fill out the NEI-VFQ 25 questionnaire at baseline and week 12. This will be filled out during a study visit. Participants will be encouraged to report any adverse effects.

All participants will be offered to contact the investigating physician should they notice any signs or symptoms related to the investigation.

## 8.4 Schedule of Visits, Measurements and Dosing

### 8.4.1 Scheduled Visits

Refer to Appendix 1 for a schedule of visits and measurements.

#### 8.4.2 Unscheduled Visits

Unscheduled visits are possible at every time and will be documented in the respective CRF.

### 8.5 Compliance with Protocol

Investigators agree to follow the protocol for the study. The study monitor will verify compliance.

### 8.6 Subject Disposition

#### 8.6.1 Completed Subjects

A completed subject is one who has not been discontinued from the study.

#### 8.6.2 Discontinued Subjects

Subjects may be discontinued prior to their completion of the study – either discontinue study medication or completely leave the study (i.e. due to loss of follow-up). Patients who discontinue study medication generally should be followed through to the final visit.

Reasons for discontinuation may be:

- adverse events
- protocol violations
- lack of efficacy
- administrative reasons (eg, inability to continue, lost to follow up)
- sponsor termination of study
- other

Note: In addition, any subject may be discontinued for any sound medical reason and the study subjects are free to discontinue the study participation on their discretion.

Notification of a subject discontinuation and the reason for discontinuation will be made to IRW and/or study sponsor and will be clearly documented on the CRF.

### 8.7 Study Termination

The study may be stopped at any time by the sponsor with appropriate notification.

## **8.8 Study Duration**

16 weeks study duration, preceded by a maximum 4 week screening period.

## **8.9 Monitoring and Quality Assurance**

During the course of the study an IRW Consulting monitor, or designee, will make routine site visits to review protocol compliance, assess study drug accountability, and ensure the study is being conducted according to the pertinent regulatory requirements. The review of the subjects' medical records will be performed in a manner that adequately maintains subject confidentiality. Further details of the study monitoring will be outlined in a monitoring plan.

Regulatory authorities of domestic and foreign agencies, quality assurance and or its designees may carry out on-site inspections and/or audits which may include source data checks. Therefore direct access to the original source data will be required for inspections and/or audits. All inspections and audits will be carried out giving consideration to data protection as well as subject confidentiality to the extent that local, state, and federal laws apply.

## **8.10 Potential risks and benefits**

The aim is to test the hypotheses that DexNP eye drops improve VA in patients with DME, and are safe and well tolerated. If the hypothesis proves right, DexNP may potentially be developed further into an approved product of a new formulation of dexamethasone eye drops that can be given topically to replace intravitreal injections.

Possible risks for the patient are side effects of dexamethasone, which is a registered and widely used drug. Possible side effects from dexamethasone are cataract formation, increased IOP and infection.

In previous clinical trials conducted with DexNP eye drops, participants received the new eye drops 1 - 6 times a day for up to 12 weeks with no reported serious adverse effects. In these studies there was no noticeable cataract formation (except one case with modest progression), moderate reversible increase in IOP (reversed after discontinuation of DexNP) and no infections.

The DexNP formulation contains  $\gamma$ -cyclodextrin. Cyclodextrins are already being used in registered eye drop products. Gamma cyclodextrin has GRAS status with FDA.

Participants will have to have SD-OCT imaging, visual acuity and IOP measured regularly during the study which can cause them inconvenience i.e. need to visit the ophthalmic unit on regular basis for these evaluation and monitoring for side effects.

A significant benefit for the participating patients receiving active drug can be expected. Previous clinical data and clinical data using dexamethasone (approved and off-label) in different formulations for the treatment of ophthalmic indications showed significant clinical benefit. In

addition, participating patients will benefit from a very close and elaborated monthly monitoring of their ophthalmic conditions and their general health status. This intensive care for the health of the patients usually provides a significant benefit for the patients' overall conditions.

DexNP promises to replace in part intravitreal injections of anti VEGF drugs, which involve surgical risks such as infection, hemorrhage and injury as well as increased risk of cardiovascular events and death (Avery et al. 2016).

## 9 ADVERSE EVENTS

### 9.1 Adverse Event

An adverse event is defined as any untoward medical occurrence in a participating patient associated with the use of an investigational medicinal product (IMP) which does not necessarily have a causal relationship with IMP. An adverse event can be any unfavorable and unintended sign (e.g., an abnormal laboratory finding), symptom, or disease temporally associated with the use of an investigational product and judged by the Investigator as clinically significant.

All AEs are reported by the subject and/or in response to an open question from study personnel or revealed by observation, physical examination or other diagnostic procedures will be recorded in the source document and on the AE pages eCRF. Any clinically relevant deterioration in clinical finding is considered an AE and must be recorded. When possible, signs and symptoms indicating a common underlying pathology should be noted as one comprehensive event.

Documentation and evaluation regarding the adverse event should be made as of:

- type of event
- seriousness
- degree of severity
- duration (start - end)
- action taken
- causality with IMP
- outcome of the adverse event

For AE reporting purposes, no distinction should be made between the IMP and any reference/comparator/placebo product.

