## **3 CLINICAL HYPOTHESES**

1. Proprietary DexNP eye drops improve visual acuity and decrease central macular thickness significantly more than vehicle in patients with DME.
2. Proprietary DexNP eye drop formulation is safe and well tolerated.

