#### 9.1.1 Severity

Severity of an adverse event is defined as a qualitative assessment of the degree of intensity of an adverse event as determined by the investigator or reported to him/her by the patient/subject. The assessment of severity is made

irrespective of relationship to investigational product or seriousness of the event and should be evaluated according to the following scale:

- *Mild*: Event is noticeable to the subject, but is easily tolerated and does not interfere with the subject's daily activities.
- *Moderate*: Event is bothersome, possibly requiring additional therapy, and may interfere with the subject's daily activities.
- *Severe*: Event is intolerable, necessitates additional therapy or alteration of therapy, and interferes with the subject's daily activities.

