#### 10.6.5 Safety Analyses

All safety analyses will be performed on the safety population. The primary safety analysis will summarize ocular and non-ocular treatment-emergent AEs (TEAEs) using discrete summaries at the subject level by system organ class and preferred term for each treatment group. Ocular TEAEs will be summarized separately for all study and fellow eyes. A TEAE will be defined as occurring after the first dose of study medication. Serious adverse events and treatment-related ocular and non-ocular TEAEs will be summarized similarly. Ocular and non-ocular TEAEs will also be summarized by severity.

Slit lamp biomicroscopy and dilated indirect ophthalmoscopy measures will be summarized at each visit using discrete summary statistics.

Intraocular pressure will be summarized at each visit, using continuous and discrete summary statistics, including change from baseline and the proportion of study eyes with an increase from baseline in IOP of 10 mmHg or more and the proportion of study eyes with IOP of 30 mmHg or more.

Safety laboratory data will be summarized at each visit, using continuous summary statistics, including change from baseline.

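### Section 9.1 sets two thresholds for an adverse event, and the narrower one reaches symptoms, so mild ocular symptoms may go unrecorded

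*Combined protocol and SAP*

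**What the plan says.** Section 9.1 opens broadly. An adverse event is "any untoward medical occurrence in a participating patient associated with the use of an investigational medicinal product (IMP"), whether or not the product caused it. No significance condition is attached. The next sentence says what an adverse event can be: an unfavourable and unintended sign (an abnormal laboratory value is the example), a symptom, or a disease, "temporally associated with the use of an investigational product and judged by the Investigator as clinically significant".

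The section then asks for all AEs to be recorded, whether volunteered, given in answer to an open question, or found on examination. It adds a separate rule for findings: "Any clinically relevant deterioration in clinical finding is considered an AE and must be recorded".

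Section 9.1.1 defines the Mild grade: "Event is noticeable to the subject, but is easily tolerated and does not interfere with the subject's daily activities".

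Section 3 states the hypothesis "Proprietary DexNP eye drop formulation is safe and well tolerated", with no numerical criterion. Section 10.6.5 says "The primary safety analysis will summarize ocular and non-ocular treatment-emergent AEs (TEAEs) using discrete summaries at the subject level", and also tabulates TEAEs by severity. The safety endpoints in 10.1.3 are AEs, laboratory tests, IOP, slit lamp and ophthalmoscopy. No symptom or comfort scale is among them.

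**The concern.** The significance judgement in the second sentence attaches to signs, symptoms and diseases alike. For a laboratory value such a filter is ordinary practice, because many out-of-range results mean nothing. For a symptom it is different. The patient's report is the datum, and an event that is noticed but easily tolerated is the kind an investigator is most likely to call not clinically significant. The plan does not say what that term means for a symptom.

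Section 12 names burning in the eyes and ocular discomfort among the most common side effects of a marketed dexamethasone eye drop. The filter therefore falls on the symptoms one would most expect from a steroid drop given three times a day for 12 weeks. If such symptoms are left out, or left out at some sites and not others, the TEAE table understates them, and its Mild row becomes hard to interpret. A symptom that was never entered cannot be recovered at analysis.

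**Working it through.** The plan gives no figure for this point, so there is nothing to reproduce. The check is one of wording, followed by an illustration of scale under stated assumptions.

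**1. The thresholds in 9.1, side by side**

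| Sentence | Applies to | Condition for being an AE |
|---|---|---|
| First | Any untoward medical occurrence | None beyond association with use of the product |
| Second | Sign, symptom or disease | Temporal association and investigator judgement of clinical significance |
| Later rule | Deterioration in a clinical finding | Clinical relevance |

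**2. Does other text settle which one governs?** The instruction to record all AEs takes in only what the definition admits. The text in 8.3 encouraging participants to report any adverse effects governs what patients say, not what is entered as an AE. The Mild grade and the tabulation by severity suggest that mild events are expected, but neither states a recording rule. The question stays open.

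**3. What is captured regardless of the AE definition?**
- Slit-lamp evaluation of irritation at every visit (8.3.1), summarised under 10.6.5. It shows signs; stinging or transient blur may leave none.
- VFQ-25 item 4 (pain or discomfort in and around the eyes, with burning, itching and aching as examples) and item 19 (how far this limits activity). They are asked of every participant without an investigator filter, and 10.6.4 summarises each question score. They are collected only at baseline and Week 12 (Appendix 1), do not distinguish the study eye, and the instrument sits among the secondary efficacy endpoints.

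**4. Scale.** Inputs from the plan: 64 DexNP and 32 vehicle subjects (5.1). Assumed: the true share of subjects with a mild ocular symptom, and q, the share of those subjects in whom it is recorded, equal in both arms.

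- Expected subjects recorded = n × p × q. For example, 64 × 0.30 × 0.5 = 9.6 and 32 × 0.10 × 0.5 = 1.6.
- Recorded difference = (p_DexNP − p_vehicle) × q.
- As a gauge of how visible the difference is, two-sided 5% power = Φ[(difference − 1.96 × SE0)/SE1], with SE0 pooled and SE1 unpooled. For 30% against 10% at q = 1, the pooled rate is 22.4/96 = 0.233, SE0 = √(0.233 × 0.767 × (1/64 + 1/32)) = 0.0916 and SE1 = √(0.21/64 + 0.09/32) = 0.0781. The argument is (0.200 − 0.1795)/0.0781 = 0.263, so power is 60%.

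| q | 30% vs 10%: subjects | Difference (points) | Power | 20% vs 10%: subjects | Difference (points) | Power |
|---|---|---|---|---|---|---|
| 1 | 19.2 vs 3.2 | 20 | 60% | 12.8 vs 3.2 | 10 | 21% |
| 0.75 | 14.4 vs 2.4 | 15 | 44% | 9.6 vs 2.4 | 7.5 | 16% |
| 0.5 | 9.6 vs 1.6 | 10 | 27% | 6.4 vs 1.6 | 5 | 10.5% |
| 0.25 | 4.8 vs 0.8 | 5 | 12.5% | 3.2 vs 0.8 | 2.5 | 6% |

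A common q leaves the ratio between arms unchanged (3 and 2 respectively); only the absolute rates and the difference shrink.

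**5. A symptom never recorded.** With 0 of 64 recorded, the one-sided 95% upper bound is 1 − 0.05^(1/64) = 4.6%. If only a share q is recorded, the bound on the true rate is 4.6%/q: 9.1% at q = 0.5 and 13.7% at q = 1/3. This holds only for a class of mild symptoms sharing that q. Events judged significant pass the filter and keep the 4.6% bound.

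**The case against.** The best defence is that 9.1 never says an event counts only if it is judged significant. The governing definition is the first sentence, which has no such condition; the second is permissive and can be read as illustration. Defining a Mild grade and tabulating by severity makes little sense unless mild events are recorded. Severity and clinical significance are also separate axes: a mild event may be judged significant, so 9.1 and 9.1.1 do not contradict each other.

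The defence adds that tolerability does not rest on TEAE counts alone, given the VFQ-25 items and the slit-lamp examinations. The examiner is masked, so the filter should not favour an arm through knowledge of treatment. No tolerability criterion or test is set, so no formal conclusion moves.

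Most of this stands, and it limits the point. It does not remove it. An investigator who reads the second sentence literally has textual support for omitting mild burning. Masking guards against bias from knowing the treatment, but it does not stop a common filter from lowering both rates and narrowing the absolute difference. Nor does it make about 13 sites apply an undefined term alike. The VFQ-25 items are too sparse to replace event capture.

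**Conclusion.** The point holds as an inconsistency within 9.1. The second sentence adds a judgement of clinical significance that the first lacks, extends it to symptoms and diseases, and nothing says which prevails. The consequence is a risk that mild subject-reported symptoms go unrecorded, lowering TEAE counts in both arms and the absolute difference in the primary safety summary.

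A reader might infer more: that the protocol excludes every symptom not judged significant, that 9.1 contradicts the Mild grade, or that under-counting is established and the tolerability hypothesis rests wholly on the thinned counts. The documents support none of these, for the reasons given in the objection, and they contain no recording share from which a loss could be shown.

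The size is unknown. Every figure in steps 4 and 5 rests on assumed symptom rates and an assumed q common to both arms, and at q = 1 the effect is zero. The safety analyses are descriptive, so no test, boundary or success rule is affected. It is still worth correcting, because the loss, if it occurs, falls on expected symptoms of a topical steroid and cannot be repaired after data collection.

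**What to change.** State one threshold in 9.1. Limit the significance judgement to laboratory and examination findings, for example:

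*An adverse event may be any unfavourable, unintended symptom or disease arising in temporal association with the investigational product, whatever its severity, or any laboratory or examination finding so associated that the investigator considers clinically significant.*

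Then state that every untoward symptom or disease the subject volunteers, or mentions in answer to the open question, is recorded as an AE and graded by 9.1.1. Use the same term in the later rule on deterioration of clinical findings, so that findings have a single threshold, and cover the point in site training.

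The cost is a short text change and training, more mild entries to record and code, and a less favourable raw TEAE rate. The analyses in 10.6.5 need no change.
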